9.10. Other Safety Assessments

9.10.1. Columbia-Suicide Severity Rating Scale (C-SSRS)

For rollover subjects, the C-SSRS assessment taken from the last visit of the DS5565-A-E309, DS5565-A-E310, or DS5565-A-E311 study (i.e. End-of-Tapering) will be used as the baseline assessment for this study and hence will not be repeated by the subject at Visit 4 (Start-of-Treatment).

For all other clinic visits (not including telephone visits), the C-SSRS will be administered by the investigator or a qualified designee trained in its administration using the study-specific tablet.

The C-SSRS is a standardized instrument that was developed to assess the severity of and monitor changes in suicidal ideation and behavior.¹³ Four constructs are measured. The first is severity of ideation rated on a 5-point ordinal scale. The second is intensity of ideation, which comprises 5 items (frequency, duration, controllability, deterrents, and reason for ideation) each rated on a 5-point ordinal scale. The third is behavior rated on a nominal scale that includes actual, aborted, and interrupted attempts; preparatory behavior; and nonsuicidal self-injurious behavior. The fourth is lethality, which assesses actual attempts; actual lethality is rated on a 6-point ordinal scale, and if actual lethality is zero, potential lethality of attempts is rated on a 3-point ordinal scale.

9.10.2. Physician Withdrawal Checklist (PWC)

The PWC will be administered by the investigator or designee using the study-specific tablet at the Post-treatment Follow-up visit. In addition, the PWC will be administered by telephone 3 days after the subject's last dose of medication.

Although developed specifically to measure symptoms of benzodiazepine withdrawal,¹⁴ the PWC also has been used in studies of pregabalin.^{15,16,17} The PWC rates 20 common symptoms of withdrawal. The symptoms measured are based on those that are

potentially related to benzodiazepine withdrawal: somatic, mood, cognitive, fatigue, and gastrointestinal.

Each of the 20 individual items on the PWC are rated as not present, mild, moderate, or severe. Individual items rated as mild, moderate, or severe should not be handled as individual TEAEs. Rather, for any subject with at least 1 individual item rated as mild, moderate, or severe, the investigator should report “withdrawal” as a TEAE.

In addition, the investigator should be particularly attentive to any potential TEAEs that suggest opiate withdrawal at the Follow-up visit.

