6.2.1. Start-of-Treatment Visit for Rollover Subjects

For rollover subjects, the Start-of-Treatment visit (Visit 4) will be conducted on the same day of the End-of-Tapering visit of the preceding study to avoid interruption in treatment with study drug. Signature on the informed consent document for this study should be obtained before the start of the End-of-Tapering visit (Week 14, Visit 13) of the preceding study.

It should be noted that results from safety laboratory tests from the End-of-Treatment visit of the preceding study are required to determine eligibility. Subjects will be excluded for laboratory values exceeding limits listed in Table 6.2.

Table 6.2: Required Laboratory Values (from the End-of-Treatment Visit of the Preceding Study)

Blood chemistry	AST (SGOT)	> 2.0 × ULN
	ALT (SGPT)	> 2.0 × ULN
	Alkaline phosphatase	> 1.5 × ULN
	Total bilirubin	> 1.2 × ULN ^a
	Blood urea nitrogen	> 1.5 × ULN
	Creatine kinase	> 3.0 × ULN
	Serum creatinine	> 1.6 mg/dL (> 141.4 μmol/L)
	Calculated CrCl	< 60 mL/min

^a If a subject has total bilirubin > ULN: unconjugated and conjugated bilirubin fractions should be analyzed and only subjects documented to have Gilbert's syndrome may be enrolled.

Abbreviations: ALT (SGPT) = alanine aminotransferase, AST (SGOT) = aspartate aminotransferase,
CrCl = creatinine clearance (determined by the central laboratory using the Cockcroft-Gault equation),
ULN = upper limit of normal

The following activities and/or assessments will be performed at/during the Start-of-Treatment visit (Visit 4) in this study:

- Obtain written informed consent (before the start of the End-of-Tapering visit in the preceding study)
- Assess all applicable inclusion and exclusion criteria
- Perform complete physical examination (Section 9.9.2)
- Perform a 12-lead ECG (Section 9.8)
- Ask subject to complete the HADS, SF-36 and EQ-5D questionnaires
- Contact IXRS to register the subject and obtain new study medication wallet number
- Dispense study medication and review dosing instructions. The first dose of study medication is to be taken on the same day as the Start of Treatment visit, at bedtime after completion of the study visit. Subjects should be instructed to bring their study medication wallet with them to each clinic visit

Information collected during the preceding study will also be utilized in this extension study. This information includes:

- Demographic information (collected at Screening of the preceding study)

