6.3. On-Treatment Period (Visits 5 to 20; Weeks 1 to 48)

The following activities and/or assessments will be performed at all On-Treatment visits (except where otherwise noted):

- Assess for and record AEs
- After 3 weeks on the 15 mg QD dose (at Visit 6, Week 3), subjects will be asked about the adequacy of their pain control and may be dose-escalated to DS-5565 15 mg BID (see Section 5.1.1)
- Assess for and record concomitant medication use including allowable analgesics
- Review instructions with the subject for completion of the pain and sleep interference diary. Note: These instructions need to be reviewed with the subject only at Visit 10 (Week 11), Visit 13 (Week 20), Visit 16 (Week 32), Visit 19 (Week 44), and Visit 20 (Week 48)
- Review electronic diary data from the previous week. Note: These data need to be reviewed only at Visit 11 (Week 13), Visit 14 (Week 24), Visit 17 (Week 36), Visit 20 (Week 48), and Visit 21 (Week 52)
- Collect study medication wallets and review medication compliance
- Record vital signs (temperature, heart rate, supine and orthostatic blood pressure) and body weight
- Complete the C-SSRS and evaluate for continued eligibility (See Section 9.2.1)
- Perform an abbreviated physical examination for all subjects; perform a funduscopy examination without pupil dilation or a scanning laser ophthalmoscopy examination at Visit 14 (Week 24) for de novo subjects (see Section 9.9.2)
- Collect non-fasting blood and urine samples for evaluation of standard laboratory safety tests (chemistry, hematology, and urinalysis). The central laboratory will perform a serum pregnancy test on all female subjects regardless of child-bearing potential
- Contact IXRS and obtain new study medication wallet number (as needed)
- Dispense study medication and review dosing instructions. At Visit 20 (Week 48), subjects should be instructed to take all study medication, as scheduled, up until the day of their End-of-Treatment visit (Visit 21, Week 52), but not on the morning of Visit 21 (i.e. subjects should complete dosing on the evening prior to their End-of-Treatment visit)

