6.4. End-of-Treatment/Early Termination (Visit 21; Week 52)

The following activities and/or assessments will be performed at the End-of-Treatment or Early Termination visit (Visit 21). No fasting is required prior to the End-of-Treatment visit.

- Assess for and record AEs
- Assess for and record concomitant medication use including allowable analgesics
- Review electronic diary data and collect electronic diary
- Collect study medication and review medication compliance
- Record vital signs (temperature, heart rate, supine and orthostatic blood pressure) and body weight
- Collect blood and urine samples for evaluation of standard laboratory safety tests (chemistry [hematology, and urinalysis). The central laboratory will perform a serum pregnancy test on all female subjects regardless of child-bearing potential
- Ask the subject to complete the PGIC, HADS, SF-36 and EQ-5D questionnaires
- Complete the C-SSRS (See Section 9.2.1)
- Perform complete physical examination for all subjects, including a fundoscopy examination with pupil dilation or a scanning laser ophthalmoscopy examination for de novo subjects only (see Section 9.9.2)
- Perform a 12-lead ECG (Section 9.8)
- Update IXRS with subject status

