6.5. Follow-Up

6.5.1. Post-Treatment Follow-Up (Visits 22 to 24; Weeks 52 to 56)

6.5.1.1. Telephone Contact at Day 3 of Follow-up (Visit 22; Week 52.5)

All subjects, including those who discontinue prematurely, will be contacted by telephone 3 days after the subject's last dose of study treatment. The following activities and/or assessments will be performed at this 3-day follow-up telephone contact:

- Assess for and record AEs
- Assess for and record concomitant medication use including allowable analgesics
- Administer the PWC

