6.5.1.2. Visit at Week 2 of Follow-up (Visit 23; Week 54)

All subjects then will return to the clinic for post-treatment follow-up approximately 14 (\pm 3) days following the last dose of study medication.

The following activities and/or assessments will be performed at the Follow-up clinic visit (Visit 23, Week 54):

- Assess for and record AEs
- Assess for and record concomitant medication use including allowable analgesics
- Record vital signs (temperature, heart rate, supine and orthostatic blood pressure) and body weight
- Perform urine pregnancy test on all WOCBP and confirm negative
- Administer the C-SSRS(See Section 9.2.1)
- Administer the PWC

Any abnormal findings (including abnormal laboratory values) observed at the End-of-Treatment visit should be rechecked at the Follow-up visit. Further safety assessments may be required for clinically significant abnormal findings observed at the Follow-up visit.

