11.6.1. Adverse Event Analyses

AEs will be tabulated using the Medical Dictionary for Regulatory Activities (MedDRA) classification system. A TEAE is defined as an AE that emerges during treatment (having been absent prior to treatment) or worsens relative to the pre-treatment state. For subjects who transfer directly into this study from a preceding study (DS5565-A-E309, DS5565-A-E310, DS5565-A-E311), an AE that started in the preceding study will not be considered treatment-emergent in this study unless the AE worsens in severity during this study. The frequency of subjects experiencing a specific TEAE will be tabulated by system organ class, preferred term, seriousness (see Section 9.3.2), worst severity (see Section 9.3.3), and relationship to study drug (see Section 9.3.4). AEs of special interest

(defined in the SAP) will be summarized separately. In the by-subject analysis, a subject having the same event more than once will be counted only once. Listings of deaths, SAEs, and AEs leading to treatment discontinuation of a subject will be presented.

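### Any PWC item rated mild or worse after stopping is reported as 'withdrawal', and no PWC is taken before stopping to show which symptoms were already there

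*Combined protocol and SAP*

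**What the plan says.** Section 3.1.3 lists the PWC among the components of the primary safety endpoint. Section 9.10.2 describes 20 items on a four-level scale from not present to severe, covering symptoms "potentially related to benzodiazepine withdrawal: somatic, mood, cognitive, fatigue, and gastrointestinal". Items are not to become separate TEAEs. Instead, "for any subject with at least 1 individual item rated as mild, moderate, or severe, the investigator should report" one TEAE with the term 'withdrawal'.

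The PWC is scheduled twice, both times after dosing has ended:

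- Section 6.5.1.1: "All subjects, including those who discontinue prematurely, will be contacted by telephone 3 days after" the last dose, and the PWC is part of that call.
- Section 6.5.1.2: the clinic visit about 14 days after the last dose lists "Administer the PWC".

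Table 17.1 marks the PWC only in the follow-up columns. For Visit 21, Section 6.4 says "Ask the subject to complete the PGIC, HADS, SF-36 and EQ-5D questionnaires" and adds the C-SSRS, but not the PWC. The PWC is also absent from Sections 6.2.1, 6.2.2 and 6.3. Section 6.2.1 says "Information collected during the preceding study will also be utilized in this extension study", but the list that follows contains no PWC.

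On analysis, Section 11.6.7 promises only a listing and a summary, with no reference value or change score. Section 11.6.1 tabulates TEAEs by, among other things, worst severity and relationship to study drug.

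**The concern.** Withdrawal means a change that follows stopping. The rule looks only at the state after stopping and treats any symptom found there as the change.

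Overlap with symptoms already present is plausible. The five PWC symptom groups are broad. Section 1.3 anticipates dizziness and somnolence on drug, and exclusion 14 lets de novo subjects enter with mild to moderate depression or anxiety disorders. The protocol names the symptom groups but not the 20 items, so the overlap cannot be confirmed item by item.

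Section 1.3 names abrupt discontinuation as a caution for the drug class. In this study "subjects should complete dosing on the evening prior to their End-of-Treatment visit", and Sections 6.3 and 6.4 describe no taper, so the study should be informative about stopping after a year of treatment. The reported withdrawal rate would instead mix true withdrawal, continuing fibromyalgia symptoms and lingering side effects.

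**Working it through.** The plan states no figure on this point, so there is none to reproduce.

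**Step 1: rule against schedule.** Take a subject with one item at mild throughout treatment and still at mild on Day 3. Section 9.10.2 asks for 'withdrawal' to be reported. No PWC score from before stopping exists to show that nothing changed.

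**Step 2: could something else supply the reference?**

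- AE records: Section 9.1 has subjects questioned in general terms, without prompting for particular symptoms. A 20-item checklist can pick up mild symptoms that such questioning misses.
- HADS, SF-36 and EQ-5D at Visit 21: these do not correspond item by item to the PWC.
- A control group: none (Section 3.2.2).
- The detailed SAP announced in Section 11.2: it can relabel a count, but cannot create a score that was never taken.

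**Step 3: how large could the overcount be?** From Section 9.10.2: 20 items, threshold of at least one. Assumed, because the documents give no rates: each item is present in a share *p* of subjects whether or not they stop; items are either independent or correlated 0.5; true withdrawal *w* is 10% and unrelated to background.

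- Independent items: b = 1 − (1 − p)^20. For p = 5%, b = 1 − 0.95^20 = 64.2%.
- Correlated items (one-factor normal model, t = Φ⁻¹(p)): b = 1 − ∫ φ(z) [1 − Φ((t − √0.5·z)/√0.5)]^20 dz, by numerical integration.
- Reported rate: r = b + (1 − b)w. For p = 5% and independent items, r = 64.2% + 35.8% × 0.10 = 67.7%.

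| p per item | b, correlated 0.5 | b, independent | r at w = 10%, correlated | r at w = 10%, independent |
|---|---|---|---|---|
| 0% | 0% | 0% | 10% | 10% |
| 1% | 10.5% | 18.2% | 19.4% | 26.4% |
| 2% | 17.9% | 33.2% | 26.1% | 39.9% |
| 5% | 33.9% | 64.2% | 40.6% | 67.7% |
| 10% | 51.6% | 87.8% | 56.5% | 89.1% |

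Here b is the share meeting the rule with no withdrawal at one administration. Symptoms that simply persist give the same b over both administrations; symptoms that come and go would raise it.

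**Step 4: after the fix.** If symptoms only persist, the falsely labelled share falls from b to 0. With p = 5% and an assumed 1% new onset per item (independent items), the rule as written reports 1 − (0.95 × 0.99)^20 = 70.7%. Counting only items absent at Visit 21 gives 1 − (1 − 0.95 × 0.01)^20 = 17.4%. The share with any true new onset is 1 − 0.99^20 = 18.2%. The small shortfall arises because an onset on an item already present is not seen unless the grade rises.

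**The case against.** The strongest defence is that little is lost. This is an uncontrolled, descriptive study, and overcounting is the cautious direction for a safety screen. Item-level ratings at both time points are kept under Section 11.6.7. TEAEs are split by severity and relatedness, and Section 9.3.4 allows a rating of not related when the disease under study explains the event. Section 9.3.1 leaves it to the investigator to decide what is an AE, and Section 9.10.2 says *should*, not *must*. All of this stands, and it confines the problem to one AE term rather than to the whole PWC summary. But a withdrawal event rated mild and not related is still tabulated as withdrawal, Section 9.10.2 is the more specific instruction, and none of these provisions supplies an on-drug reference.

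The size is also open to challenge. Every rate is assumed, and the top figures need 20 independent items at 10% each, which is implausible for symptoms in shared groups. Exclusion 14 concerns de novo subjects only, so it says nothing about rollover subjects.

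Three stronger readings are tempting, but the documents do not support them:

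- A reader might infer that Section 9.10.2 contradicts Section 11.6.1, where "A TEAE is defined as an AE that emerges during treatment (having been absent prior to treatment) or worsens relative to the pre-treatment state". The reported event is withdrawal, which is normally absent before treatment, so the definition is met. Its reference is also the state before treatment: a symptom that began on drug would itself be treatment-emergent. Section 11.6.1 fails to filter the overcount; it does not conflict with the rule.
- A reader might infer a distorted comparison of withdrawal rates between groups. Section 11.6.7 specifies no grouping, and there is no control arm.
- A reader might infer that repeated PWC assessments during treatment are needed. One score at the end of treatment addresses the defect.

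**Conclusion.** The any-item rule and the post-dose-only schedule together overcount withdrawal, and the data to be collected cannot undo it. The direction is certain if Section 9.10.2 is followed as written, because carried-over symptoms can only add to the count. The size is unknown. Over the assumed per-item background of 1% to 10%, about 10% to 52% of subjects (correlation 0.5) or 18% to 88% (independence) would meet the rule without withdrawal, and none would if there is no background. The point affects the interpretation of one reported AE term within a primary-endpoint component. It does not put subjects at risk or invalidate the item-level PWC data. It should be changed, because the remedy is small.

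**What to change.** 1. In Section 6.4 and Table 17.1, add the PWC at Visit 21/Early Termination.
2. In Section 9.10.2, report 'withdrawal' only when an item is new or at least one grade worse than that score.
3. In Section 11.6.7, show change from that score at Day 3 and Week 2, and keep the any-item count as a secondary display.

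If the schedule cannot change, remove the any-item reporting rule and label the count 'any PWC symptom after stopping'. That needs only a change of text.

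The cost is a protocol amendment and one 20-item form at an existing visit, on the tablet already in use. Three limits remain:

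- Side effects on drug, such as somnolence, may mask a withdrawal symptom and cause some undercounting.
- For completers, Visit 21 follows the last evening dose by about a day. An Early Termination score may come later: Section 4.2.2 asks for that visit as soon as possible after withdrawal, and Section 4.2.1 withdraws subjects who have missed more than 7 consecutive days of dosing. Flag scores taken after the last dose at Early Termination and show those subjects separately.
- A return of fibromyalgia symptoms after stopping cannot be fully separated from withdrawal.

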10. OTHER ASSESSMENTS

Not applicable.

11. STATISTICAL METHODS

11.1. Analysis Sets

The following analysis sets will be used to summarize the data from this study:

- The enrolled analysis set will include all subjects who signed the ICF and were enrolled into the study
- The safety analysis set will include all subjects who received at least 1 dose of study medication.

11.2. General Statistical Considerations

The statistical package SAS[®] (Version 9.2 or higher) will be used to produce all summary tables and figures and data listings.

Raw data will be presented with the same precision with which they were collected.

For summary statistics, means and medians will be displayed to one more decimal place than was determined for raw data, dispersion statistics will have two more decimal places, and the minimum and maximum will be displayed to the same number of decimal places as the raw data.

Quantitative data will be tabulated with descriptive summary statistics: arithmetic mean, standard deviation, median, minimum and maximum values, and number of observations. For categorical data, frequency tables will be provided.

For variables expressed as percent, the denominators for the calculation of percentage will be the number of subjects who had that variable assessed.

A detailed SAP describing the methodology to be used in the final analysis will be prepared before data unblinding. A change in the planned statistical analysis will require a protocol amendment only if it substantively alters the principal features of the protocol. Any deviations from the planned statistical analyses in the protocol will be fully described in the SAP.

11.3. Study Population Data

Demographic characteristics will be summarized for the enrolled analysis set according to treatment assignment in the preceding study (as applicable). Continuous demographic variables (age [calculated from date of birth to the date of first dose], weight, height, and body mass index) for all enrolled subjects will be summarized with descriptive statistics. Categorical demographic variables (gender, race, ethnicity, and age group [e.g. non-elderly, elderly, very elderly]) will be summarized with frequency counts and corresponding percentages.

Subject disposition will be summarized for the enrolled analysis set according to treatment assignment in the preceding study (as applicable). The number of subjects screened, the number enrolled, and the number and percent of those who completed the

open-label extension period or withdrew (with the latter summarized by reason for withdrawal) will be summarized.

Concomitant medications will be summarized by number and percent of subjects for each World Health Organization (WHO)-Drug preferred base name and Anatomical Therapeutic Chemical category.

11.4. Efficacy Analyses

For ADPS, absolute values and changes from baseline will be summarized using the safety analysis set.

For PGIC, the proportions of subjects who are “minimally improved or better” (i.e. score ≤ 3) and of subjects who are “much improved or better” (i.e. score ≤ 2) will be summarized using the safety analysis set.

For the HADS, absolute values and changes from baseline for the Depression and Anxiety subscales will be summarized using the safety analysis set.

For the EQ-5D, absolute values and changes from baseline for the EQ-5D single summary index (based on the 5 domain questions) and the EQ VAS will be summarized using the safety analysis set.

For the SF-36, absolute values and changes from baseline for eight domains (i.e. physical functioning, role-physical, bodily pain, general health, vitality, social functioning, role-emotional, and mental health) as well as PCS and MCS scores will be summarized using the safety analysis set.

